GERD	gastroesophageal reflux disease
GI	Gastrointestinal
GSRS	Gastrointestinal Symptoms Rating Scale
H2RA	histamine-2 receptor antagonist
HCl	Hydrochloride
HS	heartburn severity
ICF	informed consent form
ICH	International Conference on Harmonisation
IRB	Institutional Review Board

IWRS	interactive web response system
LDL-C	low-density lipoprotein cholesterol
LSM	least-square mean
MedDRA	Medical Dictionary for Regulatory Activities
mITT	modified Intent-to-Treat
mRESQ-eD	modified Reflux Symptom Questionnaire Electronic Diary
NRS	numerical rating scale
PDA	personal digital assistant
PID	patient identification
PP	Per-Protocol
PPI	proton pump inhibitor
QD	once daily
QIDS-SR-16	Quick Inventory of Depressive Symptomatology (16 Item) Self Report
SAE	serious adverse event
SAP	statistical analysis plan
SF	short form
SOC	system organ class
TEAE	treatment-emergent adverse event
US	United States
WHSS	weekly heartburn severity score
WRFS	weekly regurgitation frequency score

1. INTRODUCTION

1.1 BILE ACIDS AND GERD

Bile acids play an important role in the digestive process; however, data from nonclinical and mechanistic studies suggest that the prolonged presence or excess of bile acids in the stomach and esophagus can result in toxic effects on regional tissues (1,2,3,4). Duodenogastroesophageal reflux (DGER), which contains bile acids, is thought to produce symptoms such as retrosternal pain, heartburn, nausea, and vomiting (5,6), and is associated with more severe esophageal pathology in patients with gastroesophageal reflux disease (GERD) and Barrett's esophagus, a precancerous change in the esophagus (4,7).

Gastroesophageal reflux disease is a chronic and common medical disorder with a prevalence estimated at approximately 20% to 40% in Western countries (8), and is associated with rising healthcare utilization and cost (9). Currently, proton pump inhibitors (PPIs) are the standard of care for GERD; however, it is estimated that approximately 10% to 40% of GERD patients remain symptomatic on standard-dose PPI therapy (10). DGER is hypothesized to be a potential cause of incomplete symptom response in patients who continue to experience bothersome GERD symptoms despite treatment with PPIs (11).

There is significant evidence to support DGER as a putative mechanism for persistent GERD symptoms. Pathological bile acid reflux occurs in approximately 65% of patients who continue to experience bothersome GERD symptoms despite treatment with PPIs and is hypothesized to be a cause of their incomplete symptom response (11). There is considerable clinical and nonclinical evidence that bile acid can cause esophageal damage both in conjunction with stomach acid as well as independently (1,2,5).

There is currently no widely used diagnostic technique for evaluating the role of bile acid salts in the presence of GERD that is refractory to standard dose PPIs. In this study we require patients to have esophageal erosions demonstrated by EGD or to have acid reflux confirmed by the use of the Bravo device inserted at the time of the EGD.

The Bilitec® device can be placed in the esophagus and uses the spectrophotometric analysis of the presence of bilirubin as a marker for the presence of bile acid salts that might be contributing

to reflux. It was demonstrated that bilirubin content detected by this device correlates with the concentrations of pancreatic enzymes in aspirated refluxate, suggesting that bilirubin is a good tracer for DGER (12). Therefore it is reasonable to correlate the results of Bilitec testing with the response to IW-3718 in a subgroup of patients selected to have this testing, along with the other procedures outlined in this protocol.

1.2 IW-3718

Ironwood is developing IW-3718 for the treatment of symptomatic GERD not completely responsive to PPIs and for and other gastrointestinal (GI) disorders. IW-3718 is colesevelam hydrochloride (HCl), a bile acid sequestrant (BAS).

Colesevelam HCl (hereafter referred to as colesevelam) is an orally administered, nonabsorbed, nondigestible polymer that binds bile acids in the GI tract. Colesevelam was approved in 2000 in the United States (US) as the active ingredient in Welchol™, and is indicated as an adjunct to diet and exercise for reduction of elevated low-density lipoprotein cholesterol (LDL-C) in adults with primary hyperlipidemia. Colesevelam is currently available as an immediate-release formulation only.

IW-3718 tablets are formulated as a controlled-release, solid oral dosage form intended to extend the release of the drug substance, colesevelam, into the stomach. The released colesevelam is expected to bind bile acids that are refluxed into the stomach and upper duodenum, forming a bile acid-colesevelam complex and preventing the free bile acids from entering the esophagus. The bile acid-colesevelam complex will travel down the GI tract and be excreted without being absorbed.

The controlled-release formulation in IW-3718 tablets is based on Depomed's Acuform® technology which utilizes swelling polymers to allow the tablet to be retained in the stomach for approximately 9 hours when dosed in the fed state, during which time the tablet slowly releases the active ingredient in the stomach and upper GI tract. The tablet's active ingredient is steadily delivered to the stomach and upper GI tract in a near zero-order manner. The technology is used in the formulation of 5 Food and Drug Administration (FDA)-approved drugs: Glumetza® (metformin HCl, extended release), Janumet® XR (sitagliptin and metformin HCl extended-

release), Proquin® XR (ciprofloxacin HCl monohydrate, extended release), NUCYNTA® ER (tapentadol extended-release tablets), and once-daily Gralise™ (gabapentin) tablets.

Colesevelam is not systemically absorbed and does not interfere with systemic drug metabolizing enzymes. Distribution of colesevelam is limited to the GI tract and elimination occurs through fecal excretion.

Colesevelam reduces serum LDL-C concentrations by binding bile acids in the intestine, impeding their reabsorption. As the bile acid pool becomes depleted, the hepatic enzyme, cholesterol 7- α -hydroxylase, is upregulated, which increases the conversion of cholesterol to bile acids. This causes an increased demand for cholesterol in the liver cells, resulting in the dual effect of increasing transcription and activity of the cholesterol biosynthetic enzyme, HMG-CoA reductase, and increasing the number of hepatic LDL receptors. These compensatory effects result in increased clearance of LDL-C from the blood, resulting in decreased serum LDL-C concentrations. Serum triglyceride concentrations may increase or remain unchanged. The mechanism by which colesevelam improves glycemic control is unknown. However, increasing evidence suggests that colesevelam, as a BAS, may function by signaling molecules in the liver and GI tract for lipid and glucose metabolism (13,14,15,16). The mechanism by which colesevelam is expected to reduce symptoms in GERD is by binding bile acids that are refluxed into the stomach and preventing the free bile acids from entering the esophagus and reacting with the esophageal mucosa.

There are no reported clinical efficacy studies with colesevelam in patients with GERD, or other upper GI disorders.

Colesevelam (as Welchol) has been evaluated for safety in clinical studies and via post-marketing pharmacovigilance. In general, colesevelam was safe and well-tolerated in adults with hyperlipidemia or type 2 diabetes mellitus, and in adolescents with familial hypercholesterolemia. Due to the large doses required for lipid lowering, and its local effects in the GI tract, most of the adverse events (AEs) related to colesevelam are GI in nature (constipation, flatulence, and dyspepsia). Most of these AEs were of mild or moderate intensity. In clinical lipid-lowering studies, the incidence of dyspepsia was greater at the higher doses (3.8 and 4.5 g/day).

IW-3718 has been evaluated in a Phase 2a study. This study was a 4-week, randomized, double-blind, placebo-controlled, proof-of-concept study in patients with GERD not completely responsive to QD PPI therapy. In this study patients were randomized in a 1:1 fashion to either IW-3718 1000 mg bid or placebo. A Bilitec procedure was performed as an optional procedure. Esophageal duodenogastroduodenoscopy and pH monitoring were not required, but results were collected if these procedures were performed prior to randomization or in the recent past. Symptoms were assessed over the four week period to determine severity of heartburn-related symptoms.

Safety and efficacy data are available for 93 patients, 46 of whom received 1000 mg IW-3718 BID. IW-3718 was well tolerated among patients with GERD. There were no deaths or study medication-related serious adverse events (SAEs). Common TEAEs (>5% of patients) among patients who received IW 3718 or placebo included constipation (13% vs 0%) and abdominal pain (7% vs 2%).

In this study, among all patients (Intent-to-treat [ITT] Population), severity of daytime heartburn showed a trend toward being numerically reduced in IW-3718 patients compared to placebo ($p=0.124$). The largest differences between IW-3718 and placebo for this parameter were seen in patients who underwent Bilitec monitoring. Improvements were also observed for nighttime heartburn severity at Week 4. A greater percentage of IW-3718-treated patients (9 patients, 19.6%) reported an absence of heartburn during Week 4 compared with those receiving placebo (5 patients, 10.6%).

2. STUDY OBJECTIVES

[figure not shown]
The objectives of this study are to evaluate the safety, efficacy, and dose-response relationship of IW-3718 administered orally to patients who have GERD and continue to experience GERD symptoms while receiving once-daily (QD), standard-dose PPIs.

3. INVESTIGATIONAL PLAN

3.1 OVERALL STUDY DESIGN AND PLAN: DESCRIPTION

This is a multicenter, randomized, double-blind, placebo-controlled, parallel-group, 8-week study, consisting of 3 distinct periods as illustrated in [Figure 1](#). The study will enroll patients who have GERD and continue to experience GERD symptoms while receiving QD, standard-dose PPI therapy. Eligible patients will continue to take their PPI and will be randomized to placebo or to 500 mg IW-3718 twice daily (BID), 1000 mg IW-3718 BID, or 1500 mg IW-3718 BID. Randomization will be stratified by whether they have, or do not have, erosive esophagitis on the screening esophagogastroduodenoscopy (EGD).

Figure 1. Overview of Study Design

Note: There is no Day 0

* This visit represents the end of the study

All patients will take their current PPI approximately 30-60 minutes before breakfast each day during the Screening, Pretreatment, and Treatment Periods. During the Treatment Period, all patients will take IW-3718 or matching placebo immediately upon completion of the morning and evening meal each day.

Screening Period: The Screening Period starts with the signature of the informed consent form (ICF) and is expected to last for up to 28 days. During this period, patient eligibility for entry into the Pretreatment Period will be determined. Two procedures will be required during the

Screening Period in all patients; a third procedure Bilitec® testing will be optional for all patients at selected sites (all will be done while patients continue to take their PPI):

- An EGD
- Approximately 48 to 96 hours of pH testing with the Bravo® device. If for some reason 96 hours of testing is not possible, then approximately 48 hours of testing is acceptable (Please refer to section [3.5.1.10](#) for further instruction)
- Approximately 24 hours of bilirubin detection using the Bilitec monitoring system (optional at selected sites)

Histamine-2 receptor antagonists (H2RAs) should be stopped 5 calendar days prior to the EGD and Bravo pH monitoring and antacids should be stopped 1 calendar day prior to the EGD and Bravo pH monitoring. The EGD must be performed during the Screening Period and at least 7 days before the start of the Pretreatment Period to allow time for pH collection and allow the patient to stabilize following these procedures. Upon completion of the Bravo testing, patients will refrain from using H2RAs, but may continue to use antacids if needed. Patients will continue to use their current PPI throughout the Screening Period. The end of the Screening Period coincides with the start of the Pretreatment Period

At selected sites, patients who are screened for the study with EGD and Bravo testing will also be given the option of having a Bilitec monitor inserted at that time. The Bilitec procedure is being completed in a subset of patients to collect information about whether bilirubin is present in the duodenogastric refluxate. Previous Bilitec 2000 studies have shown associations between total bile acid concentrations and Bilitec 2000 absorbance. Patients participating in the Bilitec procedure will agree to comply with a “white diet” (see [Appendix 8](#) for example “white diet”) and return approximately 24 hours later for removal of the probe. The results of the Bilitec monitoring will not affect qualification for enrollment and during participation in the study, patients will be blinded of their Bilitec testing results.

Ironwood may grant a one-week extension of the screening period window if needed for logistical delays, as described in Section [3.6.1.2](#).

Pretreatment Period: The Pretreatment Period is defined as the 14 to 21 calendar days immediately before the Randomization Visit. During this period, patients will continue to use their PPI and will refrain from using other anti-reflux medications, including antacids and H2RAs, except for the antacid that is dispensed as rescue medicine. They will also provide the following information in a handheld eDiary; they will perform at least 2 weeks of symptom assessments during which they will be required to complete daily assessments for at least 5 days each week during the 14 calendar days before the start of the Treatment Period and weekly assessments at least once during the 7 calendar days before the start of the Treatment Period in order to be eligible for randomization:

- GERD symptoms assessed once daily in the evening in the modified Reflux Symptom Questionnaire eDiary (mRESQ-eD; [Appendix 1](#))
- Dyspepsia symptoms assessed once daily in the evening using Daily Dyspepsia Symptoms ([Appendix 2](#))
- Assessment of sleep assessed once daily in the morning using Daily Assessment of Sleep ([Appendix 3](#))
- Use of per-protocol rescue medicine assessed twice daily
- Symptom relief and bothersomeness assessed once a week in the evening

Patients will be instructed to take their PPI at least approximately 30-60 minutes before breakfast each day, even on study visit days. Patients who satisfy all of the entry criteria will enter the Treatment Period.

Treatment Period: The Treatment Period begins with treatment assignment and lasts for 8 weeks. Patients will be stratified by whether they have, or do not have, erosive esophagitis on the screening EGD and randomly assigned to 1 of 4 treatments (1:1:1:1) within each stratum: placebo or 500 mg IW-3718 BID, 1000 mg IW-3718 BID, or 1500 mg IW-3718 BID. The treatment schedule will be managed by a central vendor. Enrollment will be monitored to ensure that no single center contributes > 15% of the targeted study enrollment, unless otherwise approved by the Medical Monitor. Study drug will be taken immediately after the morning and evening meals. Patients will continue to take their PPI approximately 30-60 minutes before breakfast each day and to use the eDiary to provide their daily assessments (GERD symptoms, dyspepsia symptoms, assessment of sleep), weekly assessments (weekly symptom

bothersomeness and degree of relief questions; [Appendix 6](#)), PPI compliance, and use of per-protocol rescue medicine.

For details regarding the assessments during each study period, see the Schedule of Events ([Table 2](#)).

3.2 DISCUSSION OF STUDY DESIGN, INCLUDING THE CHOICE OF CONTROL GROUPS

A double-blind, placebo-controlled, parallel-group study design was chosen in accordance with the concepts in International Conference on Harmonisation (ICH) E10, Choice of Control Groups and Related Issues in Clinical Trials (International Conference on Harmonisation of Technical Requirements for Registration of Pharmaceuticals for Human Use, 2001), in order to provide comparable treatment groups and minimal chance of selection or Investigator bias.

This study has a 14- to 21-day Pretreatment Period to establish a baseline without therapy and to familiarize patients with data collection methodology (i.e., personal digital assistants [PDAs]), and an 8-week Treatment Period to compare the test treatment with a placebo control.

3.3 SELECTION OF STUDY POPULATION

This study will be conducted in patients with GERD not completely responsive to QD PPI therapy. Approximately 260 patients will be randomized (approximately 65 patients per treatment group). The study will be conducted at approximately 60-80 study centers in the US. Optional Bilitec testing will be done at a selected number of sites participating in the protocol. The goal at these sites will be to enroll a minimum of 60 patients with Bilitec testing who are randomized to treatment with IW-3718 or placebo.

Study medication will be administered orally BID for 8 weeks; total patient participation is expected to last up to 109 days, including the Screening Period.

3.3.1 Eligibility Criteria

3.3.1.1 Inclusion Criteria

Each patient must meet all of the following criteria to be eligible for enrollment in this study:

1. Patient has signed an ICF before any study-specific procedures are performed.

2. Patient is an ambulatory, community-dwelling male or nonpregnant female and is at least 18 years old at the Screening Visit. Lactating females must agree not to breastfeed.
3. Patient has a diagnosis of GERD and reports experiencing GERD symptoms (heartburn or regurgitation) on ≥ 4 days per week during the 8 weeks before the Screening Visit while taking standard QD PPI therapy.
4. Patient has been receiving individually optimized, standard-labeled dose, QD, PPI therapy (treatment that, according to the Investigator's judgment, could not be further improved by changing the brand or timing of PPI administration) for a minimum of 8 weeks before the Screening Visit. Patients should be on a PPI dose and schedule that is consistent with the approved labeling ([Appendix 11](#)). Patients who have their PPI modified during the Screening Period may be re-screened after 8 weeks of optimized, standard-labeled dose, QD, PPI therapy provided they have not previously entered the Pretreatment Period.
5. An EGD with approximately 48 to 96 hours of pH monitoring (with a Bravo device) during the Screening Period (while the patient continues taking their PPIs) demonstrates 1 or more of the following:
 - a. Erosive esophagitis (Grade A or greater based on the Los Angeles classification of esophagitis; [Appendix 5](#)) on EGD
 - b. Evidence of pathological acid reflux (pH is < 4 for $\geq 4.2\%$ of the recording time) during at least 1 of the 24-hour time intervals of pH testing with the Bravo device
6. Patient reports heartburn severity (HS, Item #1 on mRESQ-eD) ≥ 3 (moderate) on at least 2 days and has an average HS of ≥ 2 (mild) during the last 7 days before randomization.
7. Sexually active female patients of childbearing potential (i.e., women who are not postmenopausal or who have not had a bilateral oophorectomy, hysterectomy, or tubal ligation) must agree to use 1 of the following methods of birth control from the date they sign the ICF until 24 hours after their final dose of study drug:
 - a. Hormonal contraception (i.e., contraceptive implant or injectable hormonal contraceptive)
 - b. Double-barrier birth control (e.g., condom plus intrauterine device, diaphragm plus spermicide, etc.) Patients may continue taking oral contraceptives while using one or more barrier methods.
 - c. Maintenance of a monogamous relationship with a male partner who has been surgically sterilized by vasectomy
8. Females of childbearing potential must have a negative serum pregnancy test at the Screening Visit and a negative urine pregnancy test at the Randomization Visit prior to dosing.

9. Patient agrees not to make any changes to their usual diet during the study, except those patients participating in Bilitec testing, who must agree to a “white diet” during Bilitec testing only.
10. Patient is compliant with eDiary completion; that is, they have adequately completed the eDiary questions on at least 5 days each week during the 14 calendar days before the start of the Treatment Period.
11. Patient is compliant with QD PPI dosing during the 14 calendar days before the start of the Treatment Period. Patients are considered compliant if, as reported in the eDiary, they take their PPI on at least 5 days each week.
12. Patient is fluent and literate in English or Spanish.
13. Patient is able to operate the eDiary adequately and agrees to adhere to the study requirements.
14. For patients who are receiving supplementation of a fat-soluble vitamin in order to correct or avoid a fat-soluble vitamin deficiency, the patient is willing to take the vitamin supplement at least 4 hours before taking study medication.

3.3.1.2 Exclusion Criteria

Patients who meet any of the following criteria will not be eligible to participate in the study:

1. Patient has a history of complete lack of GERD symptom response to PPIs in the past.
2. Patient reports epigastric pain or burning as his or her predominant symptom at the Screening Visit.
3. Patient has a history of gastroparesis, bowel obstruction, or is at risk for a bowel obstruction (e.g., patient has an organic GI motility disorder or a history of major GI surgery).
4. Patient has a history of serum triglycerides concentrations > 500 mg/dL on a fasting specimen, or has serum triglycerides concentrations > 500 mg/dL on a fasting specimen at Screening or any time during the Pretreatment Period.
5. Patient has a history of hypertriglyceridemia-induced pancreatitis.
6. In the Investigator's opinion, patient is susceptible to a deficiency of fat-soluble vitamins (especially vitamin D deficiency; e.g., the patient is African American or Hispanic or has osteoporosis, osteomalacia, etc.) and will be put at risk by receiving colesevelam for 8 weeks.
7. Patient has an active swallowing disorder that would prevent them from being able to swallow the study medication.
8. Patient has any alarm symptoms including but not limited to GI bleeding, anemia, vomiting, or unexpected weight loss any time during the Screening or Pretreatment Periods.
9. Patient has undergone surgery that meets any of the following criteria:

- a. Surgery of the GI tract (including gastric banding) other than an appendectomy, cholecystectomy, minor oral or rectal surgery (e.g., tonsillectomy, hemorrhoidectomy, rectocele repair) at any time before the Screening Visit
- b. An appendectomy during the 3 months before the Screening Visit or a cholecystectomy during the 6 months before the Screening Visit or minor oral or rectal surgery during the 30 days before the Screening Visit
- c. Non-GI surgery of the abdomen, pelvis, or retroperitoneal structures during the 6 months before the Screening Visit
- d. Thoracic surgery during the 6 months before the Screening Visit
- e. Other major non-GI surgery during the 30 days before the Screening Visit

10. Patient has previously undergone thoracic or abdominal radiotherapy.

11. EGD, conducted during the Screening Period, reveals that the patient has long-segment Barrett's esophagus (greater than 3 centimeters) or definite dysplastic changes in the esophagus, peptic ulcer disease, active GI bleeding, presence of symptomatic esophageal strictures, presence of esophageal or fundic varices, erosive gastritis, or eosinophilic, herpetic or candida esophagitis.

12. Patient has Gilbert's disease, Crohn's disease, diabetes mellitus, Zollinger-Ellison syndrome, pancreatitis, cholecystitis, **or** systemic sclerosis.

13. Patient has elevated (defined as > 1.5 times the upper limit of normal by the laboratory) levels of serum bilirubin at Screening or anytime during the Pretreatment Period.

14. Patient has a history of clinically significant hypersensitivity or allergies to any of the excipients contained in the study medication (active or placebo).

15. Patient has a history of cancer (resected basal cell or squamous cell carcinoma is acceptable).
Note: patients with a history of cancer are allowed provided that the malignancy has been in complete remission for at least 5 years before the Screening Visit. A complete remission is defined as the disappearance of all signs of cancer in response to treatment.

16. Patient has history of active alcoholism, drug addiction, or illicit drug use (including marijuana) during the 12 months before the Screening Visit.

17. Patient has any clinically significant finding on a physical exam, 12-lead electrocardiogram (ECG), or clinical laboratory test after signing the ICF but before receiving the first dose of study medication. (Note: The Investigator will determine if a particular finding is clinically significant. In making this determination, the Investigator will consider whether the particular finding could prevent the patient from performing any of the protocol-specified assessments, could represent a condition that would exclude the patient from the study, could represent a safety concern if the patient participates in the study, or could confound the study-specified assessments of safety or efficacy.)

18. Patient reports using a prohibited medication during the Screening or Pretreatment Periods, or is not willing or able to abide by the restrictions regarding use of prohibited medications as defined in [Appendix 4](#).
19. Patient has received an investigational drug during the 30 days before the Screening Visit, or is planning to receive another investigational drug or use an investigational device at any time during the study.
20. Patient has an acute or chronic condition that, in the Investigator's opinion, would limit the patient's ability to complete or participate in this clinical study.
21. Patient has previously entered the Treatment Period of study in which IW-3718 is a treatment.
22. Patient has previously entered the Pretreatment Period of this study.
23. Patient is enrolled in this study at another clinical study site; is an employee of the Institution or Ironwood Pharmaceuticals; or is a first-degree family member, significant other, or relative residing with an employee of the Institution or Ironwood Pharmaceuticals.

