3.4 STUDY TREATMENTS

3.4.1 Investigational Product

3.4.1.1 IW-3718

Study medication will be provided as 500 mg IW-3718 tablets which are white to off-white, oval shaped, film-coated tablets intended for oral administration. In addition to the active drug substance, colesevlam, 500 mg IW-3718 tablets contain the following inactive ingredients: microcrystalline cellulose, polyethylene oxide, colloidal silicon oxide, butylated hydroxyl

toluene, magnesium stearate, polyvinyl alcohol, polyethylene glycol, titanium dioxide, and talc. Tablets should be taken whole and never broken, crushed, or chewed.

Patients randomized to receive IW-3718 will administer the test product as follows:

- 500 mg IW-3718 BID: One 500 mg IW-3718 oral tablet plus 2 placebo oral tablets (3 tablets total) administered BID, immediately after the morning and evening meals
- 1000 mg IW-3718 BID: Two 500 mg IW-3718 oral tablets plus 1 placebo oral tablet (3 tablets total) administered BID, immediately after the morning and evening meals
- 1500 mg IW-3718 BID: Three 500 mg IW-3718 oral tablets administered BID, immediately after the morning and evening meals

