3.4.4 Method of Assigning Patients to Treatment Groups

Patients who meet all of the inclusion criteria and none of the exclusion criteria will be randomized into the study on Day 1. Patients will be stratified by whether they have or do not have erosive esophagitis on the screening EGD then randomized through central randomization in a 1:1:1:1 ratio to receive either 500 mg IW-3718 BID, 1000 mg IW-3718 BID, 1500 mg IW-3718 BID, or placebo BID.

The computer-generated randomization schedule will be prepared by an independent statistician not otherwise associated with the study.

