APPENDIX 4 PROHIBITED MEDICATIONS

All medicine listed in the sections below are excluded during the Screening, Pretreatment, Randomization, and Treatment Periods. A 1-day washout means the that the particular medicine is not allowed during the calendar day before the EGD and Bravo pH monitoring; a 5-day washout means that the particular medicine is not allowed during the 5 calendar days before the EGD and Bravo pH monitoring; a 14-day washout means that the particular medicine is not allowed during the 14 calendar days before the Pretreatment Visit.

Patients should be on a stable dose of all concomitant medications at the time of the Screening Visit and should intend to maintain their usual medication regimen throughout the study. Changes in concomitant medication regimens or use of a new concomitant medication other than as described below is not allowed during the study unless required to treat an AE or is prescribed by a physician to treat another emergent medical issue.

1-DAY WASHOUT

- Antacids
- Sucralfate

5-DAY WASHOUT

- H₂ Receptor Antagonists (prescribed or over-the-counter [OTC]) (e.g. cimetidine, ranitidine, famotidine, and nizatidine).

14-DAY WASHOUT

- Bile acid sequestrants (e.g., Welchol (colesevelam), cholestyramine, and colestipol)
- Drugs with a known drug-drug interaction or a potential for a drug-drug interaction with colesevelam (cyclosporine, levothyroxine [and other thyroid replacement therapies], olmesartan medoxomil, phenytoin, warfarin)
- Drugs with a narrow therapeutic index (e.g. warfarin, digoxin, theophylline)
- Prokinetic agents (e.g. metoclopramide, tegaserod, erythromycin); anti-cholinergic and anti-muscarinic agents (e.g. dicyclomine, flavoxate, scopolamine, hyoscyamine, propantheline, oxybutynin, tolterodine, solifenacin, darifenacin, and trospium)
[Note: inhaled ipratropium and tiotropium are permitted]

- Antipsychotic agents (e.g., risperidone, haloperidol, droperidol, chlorpromazine, perphenazine, all phenothiazines, quetiapine, olanzapine, clozapine)
- GABAergics (e.g., baclofen, valproic acid, gabapentin, pregabalin, benzodiazepine)
- Calcium channel blockers (e.g., verapamil, nifedipine, diltiazem, amlodipine, felodipine, nicardipine, nimodipine, nisoldipine)
- Beta blockers (e.g., metoprolol, timolol, atenolol, betaxolol)
- All narcotics either alone or in combination (e.g., tramadol, codeine, morphine, propoxyphene, loperamide, diphenoxylate)

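### Exclusion 14 covers allergy to the tablet excipients but does not name colesevelam, so keeping out a patient with a known reaction to the active drug rests on investigator judgement under exclusion 20

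*Protocol*

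**What the plan says.** Exclusion 14 has the same wording in the Synopsis and in protocol Section 3.3.1.2: "Patient has a history of clinically significant hypersensitivity or allergies to any of the excipients contained in the study medication (active or placebo").

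Section 1.2 identifies the drug: "IW-3718 is colesevelam hydrochloride (HCl), a bile acid sequestrant (BAS"). It adds that colesevelam has been on the US market since 2000 as a lipid-lowering product.

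Section 3.4.1.1 divides the tablet into drug substance and the rest: "In addition to the active drug substance, colesevlam, 500 mg IW-3718 tablets contain the following inactive ingredients" (the drug name is misspelled there), followed by nine names. Section 3.4.1.2 gives the same nine names for the placebo tablet.

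Among the medicines needing a 14-day washout, Appendix 4 lists "Bile acid sequestrants (e.g., Welchol (colesevelam), cholestyramine, and colestipol").

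Exclusion 20 is the general clause. It bars a patient with an "acute or chronic condition that, in the Investigator's opinion, would limit the patient's ability to complete or participate" in the study. The SAP does not restate the eligibility criteria.

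**The concern.** An allergy exclusion would be expected to cover everything in the tablet, and above all the active substance. This one names only the excipients. A site working down the list with a candidate who has a documented reaction to marketed colesevelam finds no line that says so. With about 60 to 80 centers applying the list, the outcome then depends on each investigator deciding that a general clause applies.

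What is at stake is the safety of an individual patient who might be re-exposed, under blinding, to a drug to which he or she has already reacted. No estimate or test in the plan is at stake.

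**Working it through.** The main check is textual. The only arithmetic concerns allocation.

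1. **Does the parenthesis bring in the drug substance?** In exclusion 14 it follows *study medication*, and the thing the patient must not be allergic to is still the excipients. Sections 3.4.2 and 3.4.3 use a parenthesis after *study medication* in the same way, to say that both tablet types are meant. The natural reading is therefore: excipients, whichever tablet they are in.

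2. **Is colesevelam an excipient in this protocol?** No. Section 3.4.1.1 calls it the active substance and lists the inactive ingredients separately. Comparing the two tablet descriptions:
   - IW-3718 tablet: colesevelam plus nine inactive ingredients.
   - Placebo tablet: the same nine inactive ingredients.
   - Difference between the lists: colesevelam only, which is the component that exclusion 14 does not reach.

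3. **Does another criterion cover it?** I went through all 14 inclusion criteria, all 23 exclusion criteria and Appendix 4. The nearest candidates are:
   - Exclusion 6 names colesevelam, but only in connection with fat-soluble vitamin deficiency.
   - Exclusion 17 concerns findings on examination, ECG or laboratory test after consent, not an allergy history.
   - Exclusion 18 with Appendix 4 bars use of bile acid sequestrants from the washout onward. It does not bar past use or a past reaction.
   - Exclusion 21 bars earlier participants in the treatment period of an IW-3718 study. It would catch a reaction that occurred there, but not one to the marketed product.
   - Exclusion 20 can be applied, but it does not mention allergy and turns on the investigator's opinion.

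4. **Is previous exposure possible?** Yes. The drug has been marketed since 2000 for raised LDL cholesterol, hyperlipidemia is not itself an exclusion, and past bile acid sequestrant use outside the washout window is allowed.

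5. **Allocation.** Section 3.3 plans: "Approximately 260 patients will be randomized (approximately 65 patients per treatment group"). Section 3.4.4 has patients "randomized through central randomization in a 1:1:1:1 ratio", and Section 3.1 has them "randomly assigned to 1 of 4 treatments (1:1:1:1) within each stratum". The plan's figure reproduces: 260 / 4 = 65 per group. Three of the four groups receive IW-3718, so a patient once randomized has probability 3/4 = 0.75 of receiving colesevelam, in either esophagitis stratum. This probability applies only to a patient who has already been admitted. It says nothing about how many such patients there would be.

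**The case against.** The strongest reply is that the protocol does not leave such a patient unprotected. Exclusion 20 is a criterion like any other, and a known allergy to the study drug fits it without strain. A medical history is taken at the Screening Visit (Section 3.6.1.1). Eligibility is reviewed again at the Pretreatment and Randomization Visits (Sections 3.6.1.3 and 3.6.2.1). The investigator may remove a patient when continuing is not in that patient's interest (Section 3.3.2), and the first dose is taken in the clinic (Section 3.4.6). All of this stands. A reader might infer that an allergic patient satisfies every criterion and must be accepted; the documents do not support that. What remains is that these safeguards are discretionary and that none of them names the allergy.

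A second reply is that the parenthesis adds nothing if it only labels tablet type, since both tablets have the same excipients, so it may be loose drafting for the study medication as a whole. That is possible as to intent, but it does not fit the word actually used or the separation in Section 3.4.1.1. If it was the intent, the text should say so.

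Third, the documents do not describe hypersensitivity as a risk of colesevelam. Section 1.2 says that the drug is not absorbed, that most related adverse events are gastrointestinal and mostly mild or moderate, and that the Phase 2a study, with 46 patients on IW-3718, had no drug-related serious adverse events. This is a fair reason to keep the weight of the point low. Someone who had reacted would also usually have stopped the drug long before, so the washout rule is weak evidence that such candidates will appear.

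**Conclusion.** The gap is real but small. A stated safety rule is narrower than the product it protects against: it reaches the excipients and not the active substance, and no other criterion names the omission. Exclusion of a patient with a known reaction to colesevelam therefore depends on judgement under exclusion 20.

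The documents give no frequency of colesevelam hypersensitivity. I assume 0 to a few patients among about 260. On that assumption the consequence is to individual patients and there is no effect on power.

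Two stronger conclusions might be drawn, and neither is supported:

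- That 3 × 65 = 195 of the 260 patients are exposed to this risk. That number is only the planned total for the three active groups. The number at risk is the number of allergic patients admitted, which the documents do not allow one to estimate.
- That the wording would produce an imbalance in discontinuations between active and placebo groups. This is speculative without a frequency, and at 0 to a few patients it would not be material.

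**What to change.** Reconcile exclusion 14, in both the Synopsis and Section 3.3.1.2, with the tablet description in Section 3.4.1.1, so that its scope explicitly covers all components of the study medication: the active drug substance as well as the excipients. If the sponsor already intends this, the edit only makes the text say it.

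The cost is a few words in the next protocol amendment. It needs no new procedure, because medical history is already taken at screening, and no change to the SAP. The effect on enrolment should be negligible.
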